## 1 BACKGROUND

Over the past 4 decades, allogeneic hematopoietic stem cell transplantation (allo-HSCT) from an HLA-matched donor, either related or unrelated, has been increasingly used to treat patients affected by several malignant or non-malignant disorders. However, only 25% of patients who need or could benefit from an allograft have an HLA-identical sibling and fewer than 60% of remaining patients can be matched with suitable HLA-compatible, unrelated donors (Rocha 2008). In the absence of an HLA-matched donor, alternative donor/sources of hematopoietic stem cells such as HLA-haploidentical relatives are being increasingly used. While mature donor T cells present in the graft facilitate T-cell reconstitution, in the context of increased immune genetic disparity between patient and donor, the T cells are also responsible for the occurrence of graft-versus-host disease (GVHD), a severe, sometimes fatal, immune complication, which also impairs patient's immune reconstitution.

Strategies to prevent GVHD after HLA-haploidentical allo-HSCT based on either pharmacological immunosuppression or T-cell depletion of the graft have been developed. In particular, the physical elimination of T cells from the graft has been shown to be highly effective to prevent both acute and chronic GVHD (cGVHD). However, with T-cell depletion of the graft, the patient cannot benefit from the adoptive transfer of donor-derived memory T lymphocytes, which are mainly responsible for protection from severe infections during the state of profound immune deficiency that usually lasts for at least 4-6 months after transplantation. Overall, HLA-haploidentical allo-HSCT is associated with a higher incidence of graft rejection, and both viral and fungal infections, resulting in high transplantation-related mortality (TRM).

US and European gene therapy guidelines require monitoring delayed adverse events in patients who are exposed to gene therapy products for a period of 5-15 years depending on the nature of the product. A potential, but rare, risk of gene therapy using retroviral vectors is the generation of a replication competent retrovirus. This long term follow-up observation period provides a chance to mitigate risks associated with the gene therapy.

## 2 SYNOPSIS

Study Identifier(s)	BP-404 EudraCT #2016-003226-16
Aim of the Study	This is a Phase I/II study to evaluate the long-term safety of the infusion of BPX-501 gene-modified T cells after mismatched, T cell-depleted allogeneic transplantation and evaluate disease free survival at 1 and 2 years post-transplant
Study Design	
Open label, multi-centre, non-randomized, non-controlled long-term safety evaluation
 
Follow-up of all patients enrolled on BP-004 and treated with BPX-501 who are beyond Day 180 and have completed or discontinued the parent study.

Study Population	The patient population is identical to BP-004 as it is the long-term follow-up of those patients. Estimated enrolment up to 175 BP-004 patients.
Main Inclusion Criteria	
 
1. Signed written informed consent by the patient or the patient's guardian for children who are minors
 
2. Enrolled on BP-004 protocol, received BPX-501 infusion, completed or discontinued from the study, and are beyond Day 180.
 

Main Exclusion Criteria	
 
1. Lack of parents'/guardian's informed consent for children who are minors
 
2. Withdrawal from BP-004 study prior to BPX-501 infusion.
 

Dosage, Treatment Regimen, Route of Administration	
No BPX-501 infusions will be administered under this protocol.
 
Rimiducid to be given at 0.4 mg/kg weight (intravenous infusion) only in the setting of uncontrolled GVHD.

Locations (e.g. regions)	Italy, Saudi Arabia.
Primary Endpoint(s) with Time Point(s) of Assessment	Overall Survival and incidence of Disease-Free Survival in both malignant and non-malignant patients at 1 year and 2 years post-transplant. Relapse-Free Survival in malignant patients at 1 year and 2 years post-transplant.
Main Secondary Endpoint(s) with Time(s) of Assessment	Long-term safety for a total of 15 years from BPX-501 administration

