#### **7.4.4 Preparation for Treatment**

For use, the rimiducid will be diluted prior to administration. The rimiducid is administered via intravenous (IV) infusion at a dose of 0.4 mg/kg diluted in normal saline with volume as appropriate for age of patient to be administered over 2 hours, using a DEHP-free saline bag and solution set.

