### **7.5 Infusion of Rimiducid**

#### **7.5.1 Chronic GVHD Treatment**

Chronic GVHD (cGVHD) typically occurs 100 days or later after HSCT. cGVHD can often present with a sicca-like syndrome with thickened skin, lichen planus, papules, cholestatic jaundice, scleroderma-like skin, eye and GI lesions. cGVHD patients can also develop obstructive pulmonary disease symptoms.

cGVHD is typically classified into mild (i.e., localized skin involvement, with/or without liver dysfunction) or moderate to severe (i.e., generalized skin involvement or localized skin and/or hepatic dysfunction, plus liver histology showing hepatitis/necrosis/cirrhosis, eye involvement, salivary gland involvement, or effects on other organs). Moderate to severe cGVHD usually involves more than one organ with an organ severity score of moderate or greater (or mild or greater for lungs). Management guidelines for cGVHD are shown in [Appendix B](#).

Response should be assessed per [Appendix B](#). Three general categories of overall response are used in clinical trials: complete response (CR), partial response (PR), and lack of response (unchanged, mixed response, progression). Complete response is defined as resolution of all manifestations in each organ or site, and partial response is defined as improvement in at least 1 organ or site without progression in any other organ or site. The 2014 NIH Consensus Working Group recommends that skin, mouth, liver, upper and lower GI, esophagus, lung, eye, and

joint/fascia be considered in evaluating overall response. Genital tract and other manifestations are not included due to lack of validated response measures.

Partial response in a specific organ requires an improvement of 1 or more points on a 4 to 7-point scale or an improvement of 2 or more points on a 10 to 12-point scale. The overall category of PR requires the absence of progression in any organ.

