### 9.2.3 Special Reporting Requirements for Neurotoxicity

BPX-501 cells have been documented to enter the CNS. As the significance of this finding is unknown, all CNS events with apparent encephalitis of  $\geq$  Grade 3 severity must be reported to Bellicum- within the 24 hours (SAE reporting timelines).

Refer to [Appendix E](#) for guidelines pertaining to monitoring and management of neurotoxicity.

Record all case details that can be gathered within the reporting timeframe (24 hours) on the Bellicum SAE Report Form and submit the report to [REDACTED]. Follow-up information should be collected on the SAE Report Form as soon as it becomes available and/or upon request.

Guidelines for medical management of neurotoxicity are provided in [Appendix E](#).

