## Appendix B: Management of Chronic GVHD (cGVHD)

Event	Management
cGVHD - Mild	
 
• Consider tissue biopsy to establish diagnosis
 
• Initial treatment with topical or IV steroids, or other systemic treatments (eg, calcineurin inhibitors), per institutional standard of care for mild cGVHD should be instituted. Guidelines for topical corticosteroid treatment include the following (Couriel 2006): 
 
◦ Face, axillae, and groin: lower potency steroids (hydrocortisone 1-2.5%, desonide 0.05%)
 
◦ From the neck down: mid-strength steroids (e.g., triamcinolone 0.1% cream or ointment)
 
 
 
• Systemic corticosteroids when used should be administered as methylprednisolone 2 mg/kg/day IV in a single dose; or a dose equivalent of prednisone or dexamethasone (Martin 1990; see also corticosteroid conversion table C below).
 
• If no response to steroids/systemic therapies occurs within 7 days, or there is a worsening in cGVHD, patients may then receive rimiducid: 
 
◦ Children: 0.4 mg/kg to a maximum of 40 mg IV
 
◦ Adults: 40 mg IV
 
◦ If there is evidence of clinical improvement (e.g. partial response) but not complete resolution after the first dose of rimiducid, then rimiducid may be repeated up to a total of 3 doses beginning 48 hours after the first dose, with each dose separated by 48 hours
 
◦ Daily examination on day 1 and day 2 should be performed after initiating treatment with rimiducid, then weekly for 1 month, every 2 weeks for 100 days, and monthly after 100 days post-rimiducid administration
 
◦ For new or recurrent cGVHD episodes, rimiducid may be considered for repeat administration with the above guidelines if the investigator considered rimiducid to offer clinical benefit with prior episodes.
 
 
 
• If no response to topical steroids or rimiducid, the investigator should consider other medications per institutional guidelines (eg, calcineurin inhibitors, sirolimus, mycophenolate).
 
• Peripheral blood will be used to evaluate BPX-501 cells (CD3+CD19+) at the following times: 
 
◦ Prior to administration of systemic corticosteroid doses (e.g. methylprednisolone), at 4 and 24 hours (<math>\pm</math> 30 minutes) post-systemic corticosteroid doses, and at 7, 14, 21 and 28 days (<math>\pm</math> 24 hours) post-systemic corticosteroid doses
 
◦ When possible, considering patient weight, blood samples will be drawn within 4 hours (<math>\pm</math> 30 minutes) prior to the initiation of rimiducid infusion; 30 mins (<math>\pm</math> 5 minutes) after initiation of the infusion; at 2 hours (< 5 min prior to end of the rimiducid infusion), 4 hours, 6 hours, 8 hours, 12 hours, and 24 hours (<math>\pm</math> 30 minutes) after the initiation of the infusion. Each sample collected out to 24 hours should be split for separate processing. Approximately 0.5 to 1 mL of blood should be processed to plasma and stored at -80 C for later PK analysis of rimiducid. The remaining samples, at least 0.3 mL of blood, should be analyzed locally for prompt CD3+CD19+ T cell analysis. These additional samples (at least 0.3 mL) will be drawn at 48 hours (<math>\pm</math> 30 minutes), then at 7 days (after initiation of infusion of each dose of rimiducid), and at 14 days, 21 days, and 28 days (<math>\pm</math> 24 hours) after the final dose of rimiducid (in
 
 
 

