
	
the event multiple doses are administered) and evaluated for T cell responses only.
 
 
At each evaluation, complete Chronic GVHD Activity Assessment-Clinician and Chronic GVHD Activity Assessment-Patient Self Report
 

cGVHD – Moderate to Severe	
 
Consider tissue biopsy to establish diagnosis
 
Initial treatment with IV steroids or other systemic treatments (eg, calcineurin inhibitors) per institutional standard of care for extensive cGVHD should be instituted.
 
If no response to topical steroids or rimiducid, the investigator should consider other medications per institutional guidelines (eg, calcineurin inhibitors, sirolimus, mycophenolate).
 
If no response steroids/systemic therapies occurs within 7 days, or there is a worsening in cGVHD, patients may then receive rimiducid 
 
Children: 0.4 mg/kg to a maximum of 40 mg IV
 
Adults: 40 mg IV
 
If there is evidence of clinical improvement (e.g. partial response) but not complete resolution after the first dose of rimiducid, then rimiducid may be repeated up to a total of 3 doses beginning 48 hours after the first dose, with each dose separated by 48 hours
 
Daily examination on day 1 and day 2 should be performed after initiating treatment with rimiducid, then weekly for 1 month, every 2 weeks for 100 days, and monthly after 100 days post-rimiducid administration
 
For new or recurrent cGVHD episodes, rimiducid may be considered for repeat administration with above guidelines if the investigator considered rimiducid to offer clinical benefit with prior episodes
 
 
 
Peripheral blood will be used to evaluate BPX-501 cells (CD3+CD19+) at the following times: 
 
Prior to administration of systemic corticosteroid doses (e.g. methylprednisolone), at 4 hours and 24 hours (<math>\pm</math> 30 minutes) post-systemic corticosteroid doses, and at 7, 14, 21 and 28 days (<math>\pm</math> 24 hours) post-systemic corticosteroid doses
 
As achievable, considering patient weight, blood samples will be drawn within 4 hours (<math>\pm</math> 30 minutes) prior to the initiation of rimiducid infusion; 30 mins (<math>\pm</math> 5 minutes) after initiation of the infusion; at 2 hours (< 5 min prior to end of the rimiducid infusion), 4 hours, 6 hours, 8 hours, 12 hours, and 24 hours (<math>\pm</math> 30 minutes) after the initiation of the infusion. Each sample collected out to 24 hours should be split for separate processing. Approximately 0.5 to 1 mL of blood should be processed to plasma and stored at -80 C for later PK analysis of rimiducid. The remaining samples, at least 0.3 mL of blood, should be analyzed locally for prompt CD3+CD19+ T cell analysis. These additional samples (at least 0.3 mL) will be drawn at 48 hours (<math>\pm</math> 30 minutes) and 7 days (<math>\pm</math> 24 hours) (after initiation of infusion of each dose of rimiducid), and then at 14 days, 21 days, and 28 days (<math>\pm</math> 24 hours) after the final dose of rimiducid (in the event multiple doses are administered) and evaluated for T cell responses only.
 
 
 

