**Table E.2: Management Guideline for Neurotoxicity\***

Event	Management
Grade $\geq$ 2 (Focal) 	
 
• Consider neurology consultation and performing EEG
 
• Perform daily neurological and mini-mental status examinations during hospitalizations to evaluate for resolution/worsening of symptoms
 
• Perform CNS imaging (MRI and/or contrast enhanced CT)
 
• Consider CSF evaluation for presence of cell counts (and differential), glucose, protein and gram-stain for bacteria. 
 
◦ CSF evaluations for other infectious etiologies (e.g., herpes viruses, JC virus, fungal, West Nile virus and toxoplasma)
 
◦ CSF samples should be sent to the Sponsor for research use to evaluate for the presence of BPX-501 cells
 
 
 
• Consider empiric use of anticonvulsants if seizure is expected 
 
◦ Special consideration should be considered for conditioning agents (e.g., Busulfan) or prophylactic GVHD medications (e.g., calcineurin inhibitors) as an etiology and institutional guidelines should be instituted for possible treatments (eg, prophylactic GVHD medication changes and/or treatment with seizure medications)
 
 
 
• Start management of stroke/ischemia per institutional guidelines if suspected
 
• Administration of antiviral and/or anti-fungal therapy as per institutional standard of care should be considered if infectious etiology is suspected (tailored for lab data results)
 
• A brain biopsy should be considered if other diagnostic tests are unrevealing as to an etiology.
 
• Rimiducid may be administered if CNS infection ruled out and no improvement after 48 hours of high-dose corticosteroids (1000 mg/day x 2 days for adults or 30 mg/kg/day x 2 days in children) rimiducid may be administered in conjunction with corticosteroids and anti-infective agents. Samples for PK analysis of rimiducid for research use, should be collected before and after rimiducid, including samples of the CNS for PK analysis if the patient's condition allows. If there is evidence improvement (e.g. partial response) but not complete resolution after the first dose of rimiducid, then rimiducid can be repeated every 48 hours for up to 3 doses. Please notify the medical monitor at Bellicum prior to the administration of rimiducid for neurotoxicity.
 
• Peripheral blood should be evaluated for BPX-501 cells (CD3+CD19+) at the following times: 
 
◦ Prior to administration of systemic corticosteroid doses (e.g. methylprednisolone), at 4 and 24 hours (<math>\pm</math> 30 minutes) post-systemic corticosteroid doses, and at 7, 14, 21 and 28 days (<math>\pm</math> 24 hours) post-systemic corticosteroid doses
 
◦ Within 4 hours (<math>\pm</math> 30 minutes) prior to initiation of rimiducid infusion, 30 minutes (<math>\pm</math> 5 minutes) after initiation of infusion, at 2 hours, 4 hours, 6 hours, 8 hours, 12 hours, 24 hours (<math>\pm</math> 30 minutes) (split samples). Subsequently at 48 hours (<math>\pm</math> 30 minutes), 7 days (after initiation of infusion of each dose of rimiducid), and at 14 days, 21 days, and 28 days (<math>\pm</math> 24 hours) after the final dose of rimiducid (if more than one dose is administered) blood samples will be drawn. Vital signs are recorded prior to rimiducid, and 15, 30, 60, 120 and 240 minutes (<math>\pm</math> 5 minutes) after start of infusion.
 
◦ If cerebrospinal fluid (CSF) can be safely obtained, CSF should be sent to the Sponsor for research use to evaluate for BPX-501 cells (CD3+CD19+) prior to initiation of high-dose corticosteroids or rimiducid. If a sample of CSF can be safely obtained after initiation
 
 
 

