
	
of corticosteroids and/or rimiducid for the treatment of neurotoxicity, CSF should be sent to the Sponsor for research use to evaluate for BPX-501 cells (CD3+CD19+) (see Table E.3)

Grade $\geq 2$ (Generalized) 	
 
Perform routine institutional care for patients with altered mental status/obtundation (eg, continuous vital sign monitoring, oxygen, suction, airway protection measurements and consideration of need for mechanical ventilation, ICU admission)
 
Neurology consult and EEG evaluation
 
CBC analysis and peripheral blood smear evaluation to evaluate for thrombotic microangiopathy (TTP/HUS)
 
Evaluation for electrolyte and acid-base etiologies
 
Evaluation for liver dysfunction and evidence of hyperammonemia/veno-occlusive disease (VOD)
 
Perform daily neurological and mini-mental status examinations during hospitalizations to evaluate for resolution/worsening of symptoms
 
Perform CNS imaging (MRI and/or contrast enhanced CT)
 
Perform CSF evaluation for presence of cell counts (and differential), glucose, protein and gram stain for bacteria. 
 
CSF evaluations for other infectious etiologies (eg, herpes viruses, JC virus, fungal, West Nile virus and toxoplasma)
 
CSF samples should be sent to the Sponsor for research use to evaluate for the presence of BPX-501 cells
 
 
 
Consider empiric use of anticonvulsants if seizure is expected 
 
Special consideration should be considered for conditioning agents (eg, Busulfan) or prophylactic GVHD medications (eg, calcineurin inhibitors) as an etiology and institutional guidelines should be instituted for possible treatments (eg, prophylactic GVHD medication changes and/or treatment with seizure medications)
 
 
 
Consideration of high-dose corticosteroid treatment (1000 mg/day x 3-5 days for adults or 30 mg/kg/day x 2-5 days in children) if no evidence of CNS/systemic infection
 
Consideration of empiric antiviral and/or anti-fungal therapy as per institutional standard of care should be considered if infectious etiology is suspected (tailored for lab data results)
 
A brain biopsy should be considered if other diagnostic tests are unrevealing as to an etiology.
 
Rimiducid may be administered if CNS infection ruled out and no improvement after 48 hours of high-dose corticosteroids (1000 mg/day x 2 days for adults or 30 mg/kg/day x 2 days in children) rimiducid may be administered in conjunction with corticosteroids and anti-infective agents. Samples for PK analysis of rimiducid for research use, should be collected before and after rimiducid, including samples of the CNS for PK analysis if the patient's condition allows. If there is evidence improvement (e.g. partial response) but not complete resolution after the first dose of rimiducid, then rimiducid can be given every 48 hours for 3 doses. Please notify the medical monitor at Bellicum prior to the administration of rimiducid for neurotoxicity.
 
Peripheral blood will be collected for research purposes to evaluate BPX-501 cells (CD3+CD19+) at the following times: 
 
Prior to administration of systemic corticosteroid doses (e.g. methylprednisolone), at 4 and 24 hours (<math>\pm</math> 30 minutes) post-systemic corticosteroid doses, and at 7, 14, 21 and 28 days (<math>\pm</math> 24 hours) post-systemic corticosteroid doses
 
Within 4 hours (<math>\pm</math> 30 minutes) prior to initiation of rimiducid infusion, 30 minutes (<math>\pm</math> 5 minutes) after initiation of infusion, at 2
 
 
 

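### The BP-404 protocol states two different rimiducid doses for adults, and its synopsis rules out a neurotoxicity use that Table E.2 permits

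*Protocol*

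**What the plan says.** **Dose.** The synopsis states "Rimiducid to be given at 0.4 mg/kg weight (intravenous infusion) only in the setting of uncontrolled GVHD". Section 7.4.4, which covers preparation, says "The rimiducid is administered via intravenous (IV) infusion at a dose of 0.4 mg/kg". Neither sets a maximum or distinguishes adults from children.

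Appendix B does both. Its mild row and its moderate-to-severe row each say "Children: 0.4 mg/kg to a maximum of 40 mg IV" and "Adults: 40 mg IV". Section 7.5.1 leads there: "Management guidelines for cGVHD are shown in" Appendix B. Up to three doses, 48 hours apart, are allowed.

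**Indication.** The synopsis limits use to uncontrolled GVHD. Section 9.2.3 says "Guidelines for medical management of neurotoxicity are provided in" Appendix E, and there both the focal and the generalized rows of Table E.2, for events of Grade 2 or higher, say "Rimiducid may be administered if CNS infection ruled out and no improvement after 48 hours of high-dose corticosteroids". The medical monitor must be told beforehand. The table gives the interval and number of doses (in the generalized row, "then rimiducid can be given every 48 hours for 3 doses") but no amount in mg or mg/kg.

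**The concern.** No BPX-501 is infused in BP-404, so rimiducid dosing is the one experimental intervention that investigators control. For most adults the two dose statements cannot both be followed, and whichever is used departs from the other. Section 10.5 requires every protocol deviation to be described and justified, so it would be unclear which dose counts as the deviation. For a patient with neurotoxicity, a treatment that one part of the protocol permits is excluded by another.

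Adults are foreseeable. Section 6 admits patients up to age 18, Section 7.2 follows them for 15 years after BPX-501, and Section 6.1 keeps them eligible for rimiducid. Appendix B has its own adult line, and Table E.2 splits the steroid dose between adults and children.

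This is a question of consistency. It does not challenge the choice of either dose.

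**Working it through.** **Inputs.** From the synopsis and Section 7.4.4: 0.4 mg/kg for every patient. From Appendix B: children 0.4 mg/kg up to 40 mg, adults 40 mg, at most three doses. The documents give no body weights, so those below are assumptions chosen to show the range.

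**Formulas,** with W the weight in kg:
- Rule A (synopsis, 7.4.4): dose = 0.4 × W
- Rule B, child (Appendix B): dose = min(0.4 × W, 40)
- Rule B, adult (Appendix B): dose = 40
- Adult ratio B/A = 40 / (0.4 × W) = 100 / W

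**Where the rules agree.** For adults, 0.4 × W = 40 gives W = 40 / 0.4 = 100 kg and no other weight. For children they agree at every weight up to 100 kg; at 30 kg, for example, both give 12 mg.

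**Adult dose by assumed weight:**

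| W (kg) | Rule A (mg) | Rule B (mg) | B/A |
|---|---|---|---|
| 50 | 20 | 40 | 2.00 |
| 60 | 24 | 40 | 1.67 |
| 70 | 28 | 40 | 1.43 |
| 80 | 32 | 40 | 1.25 |
| 100 | 40 | 40 | 1.00 |
| 120 | 48 | 40 | 0.83 |

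Over a full three-dose course the totals are 3 × 20 = 60 versus 3 × 40 = 120 mg at 50 kg, and 3 × 28 = 84 versus 120 mg at 70 kg.

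**Indication, side by side:**

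| Place | Chronic GVHD | Neurotoxicity | Amount stated |
|---|---|---|---|
| Synopsis | Allowed if uncontrolled | Excluded by *only* | 0.4 mg/kg |
| Section 7.4.4 | Not specified | Not specified | 0.4 mg/kg |
| Appendix B | Allowed after steroid or other systemic therapy fails, or on worsening | Not covered | Child 0.4 mg/kg to 40 mg; adult 40 mg |
| Table E.2 | Not a condition | Allowed after high-dose steroid fails | None |

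Table E.2 does not make GVHD a condition, so its permission cannot be read as a subset of the synopsis rule. Because it states no amount and does not cite Appendix B, the only dose that reaches a neurotoxicity patient is the general one in Section 7.4.4. As written, the same 50 kg adult would receive 40 mg for chronic GVHD under Appendix B and 20 mg for neurotoxicity, with no reason given. Acute GVHD, which secondary objective 2 covers, has no dose of its own either, since Appendix B is confined to chronic disease.

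No passage ranks one rule above the other. No sample-size or power figure is involved.

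**The case against.** The best defence is that the working instructions can be found. A synopsis is a summary; for chronic GVHD, Section 7.5.1 leads to Appendix B, and for neurotoxicity Section 9.2.3 and Table 1 footnote 5 lead to Appendix E. Entrants are infants, children and teenagers, and for a child up to 100 kg nothing conflicts. Notifying the medical monitor adds a check before neurotoxicity dosing.

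Most of this stands and limits the size of the point. Appendix B is probably the intended rule for chronic GVHD. It does not remove the conflict, because Section 7.4.4 is body text in the place where staff preparing the drug would look, and because nothing supplies a neurotoxicity amount.

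A reader might also infer more than the documents support:

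- *That the synopsis is simply out of date on indication.* The SAP introduction does name neurotoxicity as a use of the switch. But that SAP is based on BP-004. Its Section 4.1 describes rimiducid as a drug for GvHD, and both rimiducid populations in its Section 6.1 are restricted to GvHD treatment. It cannot show which BP-404 passage is outdated.
- *That the adults exposed to the GVHD dose conflict are limited to those aged 16 or older at transplant,* because scheduled GVHD assessments stop at month 24 (18 − 2 = 16, taking 18 as adult). Eligibility for rimiducid continues under Section 6.1, and Table 3 and Section 9.1.5 collect GVHD whatever its onset date. Month 24 bounds nothing.
- *That 40 mg is the adult dose for every indication.* No passage gives 40 mg for neurotoxicity, and Appendix B does not cover acute GVHD.
- *That the reference in Section 7.7 to Section 7.2 loses the treatment conditions.* Section 7.2 holds no rimiducid instructions, but Section 7.1 and the synopsis still require failure of standard treatment or uncontrolled disease. The reference is a clerical slip.

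**Conclusion.** The point holds as a minor inconsistency in the protocol. Two adult dose rules coexist and agree only at 100 kg; across assumed weights of 50 to 120 kg, the flat dose is 2.0 to 0.83 times the weight-based one. The synopsis restriction to GVHD cannot stand beside Table E.2, which in turn omits the amount.

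The ratios rest on assumed weights. How many adults would be treated is unknown, and the age that defines an adult is not stated. A reader might infer that one of the doses is unsafe, but the documents contain no evidence of harm from either. Children up to 100 kg are unaffected, and so are the OS, DFS and RFS analyses.

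**What to change.** 1. **Synopsis and Section 7.4.4:** replace the single 0.4 mg/kg statement with one sponsor-confirmed dose rule per indication. For chronic GVHD, use the Appendix B rule: children 0.4 mg/kg up to 40 mg, adults 40 mg. For acute GVHD and for neurotoxicity, state an explicit dose.
2. **Appendix B:** define the age at which the adult dose applies.
3. **Table E.2:** write the confirmed neurotoxicity dose into both rows.
4. **Synopsis indication:** replace the restriction with *for uncontrolled GVHD or, after notifying the medical monitor, for neurotoxicity under the conditions of Table E.2*.
5. **Section 7.7:** as a clerical correction, point to Section 7.5 and Appendices B and E in place of Section 7.2.

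The sponsor must settle the acute GVHD dose, the neurotoxicity dose and the age cut-off first, because the documents do not. The cost is that clinical decision, a short amendment, and a check that the pharmacy manual, which is not available here, agrees. No new data, visits or patients are needed.
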